### 2. Health systems leaders for Key Informant Interviews:

Health system leaders will be recruited directly through email, phone and in-person introduction to the study from among individuals who are experienced administrators and clinical heads in Zambia, from both UTH and other health facilities in Lusaka.

### 3. Community health workers (CHWs) for Interviews:

We will identify a list of eligible CHWs through the CLO coordinator. These will be UMB CHWs recruited to deliver the recharge intervention

### 4. Caregivers/Supporters of discharged HIV Patients:

We will seek to conduct in-depth interviews with caregivers of the patients recruited into our qualitative study cohort of patients for the intervention . As explained above, we will first seek the consent of the patient to invite their caregiver to participate in the study and only interview the caregiver's following their provision of their informed consent.

## **7. Data Collection & Management**

### **7.1 Study Procedures**

The research team will consist of a small group of researchers with expertise in qualitative research and fluent in English, Nyanja, and Bemba, the primary languages spoken in Lusaka Province. The research team will be trained and supervised by UMB researchers with expertise in quantitative and qualitative research. The primary methods of research will be enrollment in a study register. Qualitative procedures will include one-on-one interviews with participants identified through purposive and convenience sampling. All qualitative interviews will be conducted by trained research assistants. Following participant recruitment, IDIs will take place in a private room with the trained interviewer.

### **7.2 Data Management and Storage**

Quantitative data will be entered on a password-protected laptop and analyzed using Stata 15 (Stata, College Station, TX). Digital recordings from interviews with patients and the resulting transcriptions will be labeled only with a unique study ID and stored at Maryland Global Initiatives Corporation (MGIC) on the secure server. No personal identifiers will be captured to protect confidentiality. The database will be housed on a password-protected laptop computer owned by MGIC and will be backed up periodically to the MGIC server. Data analysis will occur both in Zambia and internationally and analysts will only work with de-identified data to protect confidentiality.

MGIC has a robust ICT department that will provide primary data management services on this study. As a key partner to MoH in the HIV/AIDS response, MGIC collects and manages HIV program data for MoH at >100 HIV care facilities in Zambia. A 5x3 meter secured room at MGIC headquarters houses central servers and 2 senior data managers plus 2 senior ICT experts are on hand to support data capture, management, and storage. On this study, as mentioned above, our qualitative and quantitative data will be backed up on the server. However, only anonymized data will be backed up.

## **8. Statistical Considerations**

### **8.1 Sampling frame and Sample Size Calculations**

#### ***8.1.1 Quantitative sample Size***

Our sample size calculation was based on the hypothesis that CHW follow-up will have substantial impact on the proportion who are alive and fully HIV virally suppressed at 6 months. To detect a change in retention from 60% (based on prior studies) to 80% between historical controls and pilot study participants, with a two-sided alpha and 80% power, we would need a sample size of at least 82 pilot participants. We expect that, because of the clinical acuity of participants, some may pass away before discharge occurs, and these would be censored and not included in main analysis. Hence, we will inflate the sample to 100.

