### **4.2 Secondary objectives**

1. To estimate the potential impact of the pilot program on the proportion who are alive and virally suppressed at 6 months post-discharge
2. To understand implementation factors related to pilot program

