### **4.5 Secondary Endpoints – HIV cascade and clinical outcomes**

1. HIV viral load at 6 months post-discharge.
2. Readmission to hospital within 6 months of discharge
3. Mortality within 6 months of discharge.
4. Retention in HIV care after discharge defined by no gap of >28 days off ART from discharge date to 6 months post-discharge date.
5. Engaged in ART care at a community (non-referral site) clinic at 6 months post-discharge
6. Mental health outcomes (i.e. depression level) post intervention

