#### **5.2.4 Quantitative outcomes:**

Our primary effectiveness outcome will be alive and virally suppressed at 6 months after hospital discharge. Patients who either pass away or have a viral load >60 copies/ml will be considered failures. Patients who are alive but have unknown VL will also be considered failures. Those who transfer care outside of Lusaka District (we expect this to be 2-3%, based on a prior study) will be censored. We will also evaluate numerous secondary outcomes, including retention on ART, defined as possession of ARVs within 30 days of the 6-month post-discharge time point, consistent with PEPFAR TX\_CURR definition. We will also assess ARV adherence (based on medication possession ratio), number of visits attended, and the rate of hospital re-admission.

To ascertain these outcomes, our research assistant will contact the client each month post-discharge to check vital status (alive versus dead) and whereabouts. At 6 months after discharge, we will confirm the location of last HIV care and arrange for patient to have HIV VL, either back at the hospital or at their local clinic. The team will extract electronic medical records from the clinic including visit, pharmacy, and laboratory data, including HIV viral load results. Transfers within Lusaka (where there are 30+ ART clinics) are common and this approach will allow us to have complete end-line data for most clients, including historical controls and pilot participants.

We will also collect implementation outcome data during the trial, such as proportion of trial participants who do not receive any CHW services, the number and type (phone calls, home visits, meetings at the facility) of interactions between participants and CHWs. Semi-structured interviews with a subset of patients will be done to check acceptability of the intervention.

To begin to understand and anticipate meaningful patterns in our pilot data, we will also collect socio-demographics and socio-economic data on patients and their households, as well as capturing extent and severity of co-morbidities. We will include the following measures, captured at the following time points:

At enrollment/in hospital:

- Education (highest completed grade attained) for patient and primary caregiver
- Age, marital status, number of children
- Relationship to household head
- Religion and religiosity (affiliation, frequency of church attendance (weekly))

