## **8.2 Data Analysis**

### ***8.2.1 Quantitative analysis***

We will describe and compare sociodemographic and clinical characteristics of historical controls and participants. For the primary outcome, we will compare proportions retained in care at 6 months between controls and CHW follow-up recipients, after excluding participants who transferred out. Potential confounders between the intervention and outcome will be adjusted for in multivariable analysis. Sex-stratified models will be fit as secondary analyses, which are important in planning for the follow-on trial. We will compare the proportions who died in each group, as our central hypothesis is that re-engagement in HIV care after hospitalization can lower mortality. We recognize that with a sample size of 100 we will be under-powered for multivariable and sex-stratified analyses (as well as the mortality comparison); however, the point estimates, when interpreted together with feasibility and acceptability data, will be informative and provide support for future use of this intervention.

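### The 82 patients and 80% power in 8.1.1 are calculated for retention, not for alive-and-virally-suppressed at 6 months, which 4.2, 5.2.4 and the opening of 8.1.1 name as the effectiveness outcome

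*Combined protocol and SAP*

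**What the plan says.** All references are to the combined protocol and SAP.

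Three places name alive-and-suppressed at 6 months:
- 4.2, first secondary objective: "To estimate the potential impact of the pilot program on the proportion who are alive and virally suppressed at 6 months post-discharge".
- 5.2.4: "Our primary effectiveness outcome will be alive and virally suppressed at 6 months after hospital discharge". Death, a viral load above 60 copies/ml, and an unknown viral load in a living patient all count as failure.
- 8.1.1, first sentence, which hypothesises a "substantial impact on the proportion who are alive and fully HIV virally suppressed at 6 months".

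Two places use retention:
- 8.1.1, second sentence: "To detect a change in retention from 60% (based on prior studies) to 80% between historical controls and pilot study participants". With 80% power this leads to "we would need a sample size of at least 82 pilot participants", which is then inflated to 100.
- 8.2.1: "For the primary outcome, we will compare proportions retained in care at 6 months between controls and CHW follow-up recipients".

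Retention is itself described in two ways. Section 4.5 and the synopsis have "Retention in HIV care after discharge defined by no gap of >28 days off ART from discharge date to 6 months post-discharge date". Section 5.2.4 places it among "numerous secondary outcomes, including retention on ART, defined as possession of ARVs within 30 days of the 6-month post-discharge time point".

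Section 5.2.2 describes the historical controls without giving a number. It says the comparison will inform the size of a later, fully powered trial.

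**The concern.** Section 8 is consistent with itself to the extent that the outcome used in the calculation is also the one analysed. But that outcome is retention, which 5.2.4 ranks as secondary. The outcome that 5.2.4 ranks as primary has no analysis in 8.2.1 and no planning rates in 8.1.1.

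A reader therefore cannot tell which comparison is the main effectiveness result or which one carries the 80% power. The choice between the two could also be made after the results are seen. The under-powering caveat in 8.2.1 covers only the multivariable, sex-stratified and mortality analyses, so it is easy to assume that the 80% extends to alive-and-suppressed.

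Two inputs to the retention calculation are also open: how many historical controls it assumes, and which description of retention the 60% refers to.

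**Working it through.** **1. Reproducing the 82.** Inputs from 8.1.1: 60% versus 80%, two-sided, 80% power. Assumed: alpha 0.05 and 1:1 allocation. The alpha value is absent from the text as extracted, which may be an extraction loss, and is not counted against the plan.

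Pooled two-proportion formula without continuity correction, mean rate 0.70:

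n per group = [1.96·√(2·0.70·0.30) + 0.842·√(0.60·0.40 + 0.80·0.20)]² / 0.20² = (1.270 + 0.532)² / 0.04 = 81.2, so 82.

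Power at 82 per group: z = (0.20 − 1.96·√(0.42/82)) / √(0.40/82) = (0.20 − 0.1403) / 0.0698 = 0.855, giving 80.4%.

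A one-sample test against a fixed 60% would need [(1.96·√0.24 + 0.842·√0.16) / 0.20]² = 42.04, so 43. The 82 is therefore a two-group, per-group figure.

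**2. Dependence on the control number.** The same test with unequal groups uses the pooled rate p = (0.60·n_c + 0.80·n_p)/(n_c + n_p), where n_c is controls and n_p is pilot patients. The 95% CI half-width is 1.96·√(0.24/n_c + 0.16/n_p). The values 67 and 50 are illustrations only.

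| Controls | Power, 82 pilot patients | CI half-width, 82 pilot patients | Power, 100 pilot patients |
|---|---|---|---|
| 82 | 80.4% | 13.7 points | 84.2% |
| 67 | 76.4% | 14.6 points | 80.2% |
| 50 | 69.9% | 16.1 points | 73.4% |

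For example, with 67 controls and 82 pilot patients p = 0.710 and z = (0.20 − 1.96·0.0747) / 0.0744 = 0.720.

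**3. Does the 80% carry over to alive-and-suppressed?** The documents give no 6-month rate for this outcome, so the rates below are assumptions. The control rates of 42% and 54% are what 60% retention would give if 70% or 90% of retained patients were suppressed (0.7·60 and 0.9·60). The first row applies the 70% to both groups (0.7·80 = 56). The other two keep a 20-point gain. Same formula, two-sided 0.05, 1:1.

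| Assumed control vs pilot | Power, 82 per group | Power, 100 per group |
|---|---|---|
| 42% vs 56% | 43% | 51% |
| 42% vs 62% | 73% | 81% |
| 54% vs 74% | 77% | 84% |

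For example, 42% vs 62% at 82 per group gives z = (0.20 − 0.1529) / 0.0764 = 0.616, or 73%. The answer depends on rates that the plan does not supply.

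**4. Are the two outcomes the same thing?** A living patient who holds ARVs near month 6 but has a viral load above 60 copies/ml, or none on record, is retained under 5.2.4 yet fails alive-and-suppressed. Section 6.3 admits patients with a viral load above the assay limit or a CD4 count of 200 or below, so unsuppressed patients are expected at entry. The two rates cannot be presumed equal.

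**The case against.** The strongest reply is that retention is loose wording for the composite. Section 8.2.1 speaks of the primary outcome and excludes patients who transferred out, which echoes the censoring of transfers that 5.2.4 sets beside alive-and-suppressed. If 60% and 80% were meant for the composite, the stated power stands and only the wording is at fault. This is possible, but the text does not establish it: 5.2.4 separates the two outcomes and 8.2.1 again speaks of patients retained in care. It is a good reason to say no more than that the power is not supported.

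Three further points stand in part:
- The two descriptions of retention carry different labels (in HIV care; on ART). One covers the whole period and the other a single time point, so both may be intended. The defect is only that 8.1.1 does not say which one the 60% describes.
- The alive-and-suppressed rates above have no source in the documents. Deaths after discharge and unknown viral loads count as failures and stay in the denominator, so more than 82 pilot patients may be evaluable. That is why power is shown at 100 per group as well.
- Feasibility and acceptability are the main goal, and 5.2.1 defers a fully powered evaluation to later. This limits the consequence but does not settle which comparison 5.2.2 means to carry forward.

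**Conclusion.** The inconsistency is in the text. Section 4.2, 5.2.4 and the first sentence of 8.1.1 agree with one another on alive-and-suppressed; the second sentence of 8.1.1 and 8.2.1 use retention. The 80% power belongs to retention at 60% versus 80%. Even there it assumes two-sided 0.05 and about 82 evaluable controls as well as 82 evaluable pilot patients. It is not supported for alive-and-suppressed.

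Two stronger readings are tempting and do not hold. A reader might infer that the 82 is miscalculated; it reproduces exactly as a per-group size. A reader might also infer that the alive-and-suppressed comparison is under-powered. The documents give no rates from which to conclude that, and some plausible assumptions give more than 80% at 100 per group.

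This should be fixed, but the consequence is limited: it concerns a secondary objective of a pilot, and matters mainly because the comparison is to inform the size of a future trial.

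**What to change.** - **8.2.1:** make alive-and-suppressed at 6 months the primary effectiveness comparison, using the failure rules in 5.2.4, with retention secondary.
- **Synopsis and 4.5:** add the composite to the secondary endpoint lists, which now give viral load and mortality separately.
- **8.1.1, power:** either give control and target rates for alive-and-suppressed with their source, and restate the power or the expected 95% CI width; or state that the 80% is for retention only and that no power is claimed for alive-and-suppressed.
- **8.1.1, numbers:** state that 82 is the evaluable number per group, and give the planned number of historical controls.
- **8.1.1, retention:** say which retention measure the 60% describes. If both measures are kept, name them distinctly throughout.

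The cost is rewording and a short recalculation. The restated power may be less favourable, and stating a control number commits the team to collecting about that many. No extra pilot patients are needed.

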#### ***8.1.2 Qualitative sample Size***

A total of 24 interviews at the start of the project will be conducted with patients recruited and another 16 at the end with some of the patients interviewed at the start. An additional 16 interviews will also be conducted with care givers of the 16 patients who will be interviewed twice. Providers such as CHWs(n=4-10) and CLOs(n=2) and hospital staff(n=6-10) will also be part of the sample for the study.

## **8.2 Data Analysis**

### ***8.2.1 Quantitative analysis***

We will describe and compare sociodemographic and clinical characteristics of historical controls and participants. For the primary outcome, we will compare proportions retained in care at 6 months between controls and CHW follow-up recipients, after excluding participants who transferred out. Potential confounders between the intervention and outcome will be adjusted for in multivariable analysis. Sex-stratified models will be fit as secondary analyses, which are important in planning for the follow-on trial. We will compare the proportions who died in each group, as our central hypothesis is that re-engagement in HIV care after hospitalization can lower mortality. We recognize that with a sample size of 100 we will be under-powered for multivariable and sex-stratified analyses (as well as the mortality comparison); however, the point estimates, when interpreted together with feasibility and acceptability data, will be informative and provide support for future use of this intervention.

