## 1. Protocol Synopsis

Full Title	Re-engagement at Discharge 2: Improving post-hospital outcomes for adults with HIV in Zambia (ReCharge 2)
Clinical Trial Phase	N/A
Principal Investigators	[name], MPH [name]
Co- Investigators	[name], PhD [name], PhD, MMed, MSc. [name] [name] [name], MMed [name] [name] [name], MMed [name], MMed [name], RNHNP
Sample Size	N = 100
Study Population	Eligible patients living with HIV hospitalized at University Teaching Hospital or Levy Mwanawasa Hospital, Lusaka, Zambia
Accrual Period	1/1/2023-6/1/2024
Study Design	Single Arm Pre/Post Pilot Study
Study Duration	2 years
Study Agent/ Intervention Description	Community health worker (CHW) follow-up after discharge from hospital
Primary Objective	1. To assess the feasibility and acceptability of CHW follow-up following hospitalization
Secondary Objectives	1. To estimate the potential impact of the pilot program on the proportion who are alive and virally suppressed at 6 months post-discharge 2. To understand implementation factors related to pilot program
Exploratory Objectives	1. To investigate barriers and facilitators to ART adherence for PLHIV following hospitalization 2. To investigate barriers and facilitators to community-based support for PLHIV following hospitalization
Primary Endpoints	1. The proportion of discharged patients who are successfully visited after discharge. 2. The proportion of discharge follow-up visits by a CHW that are comprehensive 3. The proportion of initial post-discharge visits to the ART clinic that are attended by the participant's CHW supporter.
Secondary Endpoints	1. HIV viral load at 6 months post-discharge. 2. Mortality within 6 months of discharge. 3. Retention in HIV care after discharge defined by no gap of >28 days off ART from discharge date to 6 months post-discharge date. 4. ART clinic visit within 1 month of discharge 5. Transition back to ART care at original (pre-admission) clinic

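### Section 8.2.1 analyses retention in care as the primary outcome and gives no analysis of alive and virally suppressed, which Section 5.2.4 declares the primary effectiveness outcome; Section 8.1.1 mixes the two

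*Combined protocol and SAP*

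**What the plan says.** Section 5.2.4 is explicit: "Our primary effectiveness outcome will be alive and virally suppressed at 6 months after hospital discharge". Its failure rules follow: "Patients who either pass away or have a viral load >60 copies/ml will be considered failures", and "Patients who are alive but have unknown VL will also be considered failures". Patients who transfer outside Lusaka District are censored. The same section then places among its secondary outcomes "retention on ART, defined as possession of ARVs within 30 days of the 6-month post-discharge time point". This ordering agrees with secondary objective 1, in the synopsis and Section 4.2, which is about the proportion alive and suppressed.

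Section 8.2.1 reads differently: "For the primary outcome, we will compare proportions retained in care at 6 months between controls and CHW follow-up recipients", with participants who transferred out excluded. The rest of that section covers baseline description, confounder adjustment, sex-stratified models and a comparison of deaths. Viral load, suppression and the composite do not appear.

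Section 8.1.1 states its hypothesis on being alive and fully suppressed at 6 months. Its next sentence describes the change to be detected, 60% to 80%, as a change in retention, and arrives at 82 pilot participants, raised to 100.

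Section 4.5 lists among the secondary endpoints: "Retention in HIV care after discharge defined by no gap of >28 days off ART from discharge date to 6 months post-discharge date". The synopsis gives the same definition. Both list viral load and mortality as separate endpoints, and neither lists the composite.

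**The concern.** The outcome declared as primary for effectiveness has no analysis written for it, and an outcome declared secondary is analysed under the primary label. An analyst who follows 8.2.1 as written would compute the wrong variable for secondary objective 1. That analyst would also have to choose between two retention definitions without guidance.

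Section 5.2.2 says the comparison with historical controls will inform the sample size of a fully powered future trial. If the reported result is retention while the reader takes it for suppression, or the reverse, the later trial would be planned on a rate for the wrong endpoint. The sample-size paragraph has the same ambiguity, so it cannot be used to settle which outcome was meant.

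**Working it through.** **1. The sections side by side**

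| Place | Alive and suppressed | Retention |
|---|---|---|
| Synopsis, 4.2 (objectives) | Secondary objective 1 | Not named |
| Synopsis, 4.5 (endpoints) | Not listed as a composite | Secondary; no ART gap over 28 days |
| 5.2.4 | Primary effectiveness outcome | Secondary; ARVs held within 30 days of month 6 |
| 8.1.1 | Subject of the hypothesis | Label on the 60% and 80% |
| 8.2.1 | Absent | Compared as the primary outcome |

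**2. Whether the choice of outcome can change a patient's classification**

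- Alive, ART uninterrupted, ARVs in hand at month 6, viral load above 60 copies/ml or unknown: retained under both definitions, a failure under 5.2.4.
- Off ART in months 2 to 4, refilled by month 6, alive and suppressed at month 6: not retained under 4.5, retained under 5.2.4's possession definition, a success on the composite.
- Died: a failure on the composite. Neither retention definition says how a death is counted.

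The three measures are therefore not interchangeable, and disagreement with the composite can go in either direction. The documents give no frequencies for these patterns, so neither the size nor the sign of the effect on the between-group difference can be worked out.

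**3. The plan's own figure**

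Inputs from 8.1.1: p1 = 0.60, p2 = 0.80, two-sided test, 80% power. Assumed, because not stated: alpha 0.05 and as many historical controls as pilot participants. The mean proportion is 0.70.

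Pooled two-proportion formula:

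n = [1.96 × √(2 × 0.70 × 0.30) + 0.842 × √(0.60 × 0.40 + 0.80 × 0.20)]² / (0.20)²

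= [1.96 × 0.648 + 0.842 × 0.632]² / 0.04 = (1.270 + 0.532)² / 0.04 ≈ 81.2, rounded up to **82 per group**.

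Power at n per group = Φ[(0.20 × √n − 1.270) / 0.632]. At 82 this is Φ(0.855) = 0.80; at 100 it is Φ(1.154) = 0.88.

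The arithmetic is sound under those assumptions. What is unsettled is the outcome that the two rates describe:

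- If alive and suppressed, 82 stands and only a word is wrong.
- If retention, 82 is powered for retention. Power for the composite would then need suppression rates among retained and non-retained patients in each group, and the documents give none.

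**The case against.** The strongest reply is that retention is loose wording for the 5.2.4 outcome throughout. Section 8.1.1 moves from suppression to retention in consecutive sentences, as if they were the same thing. Section 8.2.1 excludes transfers, which matches the censoring rule that 5.2.4 attaches to alive and suppressed; neither retention definition carries a transfer rule of its own. This is plausible and may well be what was intended. It does not remove the problem, because the protocol never says it and retention is a separately defined endpoint in three places (synopsis, 4.5 and 5.2.4). The claim that 8.2.1 would report a different outcome therefore holds on the literal reading only.

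A second reply is that the comparison is covered elsewhere. Section 5 names mortality, readmission, viral load and retention as secondary outcomes and says that secondary outcomes will be compared with the earlier group; 8.2.1 adds a comparison of deaths. So the components are to be compared. The composite is still not named there, and Section 5 gives no method for it.

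Third, the two retention definitions could stand as two endpoints. That is fair, but they would need separate names, and 8.2.1 would need to say which one it uses.

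Finally, the listed primary endpoints concern feasibility, and 5.2.1 makes feasibility and acceptability the main goal. This stands and limits the consequence.

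**Conclusion.** The inconsistency is real and should be fixed. Sections 5.2.4, 8.1.1 and 8.2.1 do not agree on the main effectiveness outcome, and the declared one has no written analysis. The conclusion rests on the text and needs no assumption about rates. Only the reproduction of 82 per group does, through the assumed alpha of 0.05 and 1:1 groups.

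The reach is limited to secondary objective 1 and to the use of its result in planning a later trial.

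A reader might infer three stronger things that the documents do not support:

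- **The study is underpowered for alive and suppressed.** This does not follow. If 60% and 80% are composite rates, power is as planned. If they are retention rates, power for the composite could lie above or below 80%, depending on suppression rates that are not given.
- **The two outcomes will differ by a predictable amount.** They can disagree in both directions, and the between-group difference shifts only if the net disagreement differs between groups.
- **The outcome was switched, or results will be selectively reported.** Nothing shows this. The ambiguity leaves room for a mislabelled result, and shorthand is an adequate explanation of the wording.

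**What to change.** - **8.2.1:** make the main effectiveness comparison the proportion alive and virally suppressed at 6 months, under the failure and transfer rules already in 5.2.4.
- **Synopsis and 4.5:** list that composite as an endpoint beside viral load and mortality.
- **Retention:** keep it as a secondary outcome and name the definition used. If both definitions are wanted, give them separate names. Say how deaths are counted.
- **8.1.1:** state which outcome 60% and 80% describe. If alive and suppressed, replace the word retention and keep 82. If retention, say that 82 is powered for retention and give the power for alive and suppressed with its assumptions. In either case, give the numerical alpha and the number of historical controls.

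The cost is wording. Section 5.2.4 already plans vital-status contacts, a 6-month viral load and extraction of pharmacy and laboratory records, and expects that "this approach will allow us to have complete end-line data for most clients, including historical controls and pilot participants". A short power calculation is needed only if the two rates turn out to be retention rates.
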